### **Data analysis**

The data were investigated using IBM SPSS Statistic 20.0 program. As the descriptive statistics, frequency, percentage, mean and standard deviation were used. In the adherence control of continuous variables to normal distribution, Shapiro–Wilk test was used. While independent samples t test was used in the comparison of two independent groups having normal distribution, Mann–Whitney u test was used for the non-normal distributed data. In the determination of the correlation between categorical variables, Chi-Square test was used. Since measurements were repeated twice (initial–12thweeks), p- values for continuous variables are obtained from general linear model repeated measures analysis. The group was used as the between-subject factor, and time as the within-subject factor. Mean values with their 95% confidence intervals and p- values for group, time and group × time interaction

were reported. In this way, type I error rate within- and between-groups variation was controlled. Effect size (Cohen's  $d$ ) was used for measure of the magnitude of the experimental effect. It was suggested that  $d = 0.2$  be considered a 'small' effect size, 0.5 represents a 'medium' effect size and 0.8 a 'large' effect size. The larger the effect size the stronger the relationship between two variables. Statistical significance level was accepted as  $p < .05$ .

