### **Compliance questionnaire**

Compliance Questionnaire (CQ) is a form allowing to investigate 11 different areas such as the use of medication causing maladaptation in disease management in individuals with chronic illnesses, diet, weight loss, limiting physical activity, exercise, coping with stress, alcohol use, smoking, sexual activity problems, caffeine intake and working/job life. It was developed by Marston in 1969. In the form allowing Likert-type evaluation, the participant is expected to select one of the options 0 (never), 1 (very rarely), 2 (sometimes), 3 (most of the time) or 4 (always) while expressing his/her adherence level for each adaptation area. The scores corresponding to the given expression are summed, and CQ score for each participant is determined. The maximum score is 44. High score signifies an increase in the adherence level to the disease. In the validity and reliability study, internal consistency of CQ was determined as Cronbach's Alpha value .56 and intraclass correlation coefficient value .69. In this study, the internal consistency Cronbach's Alpha value of the responses given to CQ was found as .701.

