### **First stage**

Personal Information Form and Compliance Questionnaire were applied to all patients in both groups. After anthropometric measurements, FR score was determined. The data collection forms were filled with the patients using face-to-face interview technique. The data collection process lasted for approximately 10–15 min. After the data collection, the patients in the intervention group were trained. The patients in the control group were given only standard care protocol by clinicians. During study, no training programme was given to the patients in the control group by researcher but they received a ‘Coronary Artery Disease Adherence Guide’ end of study.

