### **Second stage**

12 weeks after the first interview, the patients were interviewed again face-to-face interview technique and the forms and measurements applied initially were repeated. The content of the collected data was the same as first stage.

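### The plan lists three p-values without naming the test of training and gives no confidence interval for the between-arm difference; one baseline-adjusted week-12 CQ comparison would supply both

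*Combined protocol and SAP*

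**What the plan says.** In Data analysis, "p- values for continuous variables are obtained from general linear model repeated measures analysis". The model is described in one sentence: "The group was used as the between-subject factor, and time as the within-subject factor". The planned output is "Mean values with their 95% confidence intervals and p- values for group, time and group × time interaction", followed by the claim that "In this way, type I error rate within- and between-groups variation was controlled". Cohen's d is the effect measure, with no contrast, SD or interval stated for it. The same section says that an "independent samples t test was used in the comparison of two independent groups having normal distribution", with a Mann–Whitney test for non-normal data. It does not say which variables or visits these two tests cover.

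CQ is measured before training in both arms: under First stage, "Personal Information Form and Compliance Questionnaire were applied to all patients in both groups". Under Second stage, at 12 weeks, "the forms and measurements applied initially were repeated". Baseline CQ is therefore available for every analysed patient, but it enters the model only as the first level of time.

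Setting and samples sizes the trial on CQ scores: at least 26 per group for α = .05, power .80 and effect size .80. It names neither the test nor the SD behind the .80. The analysed sample is 30 intervention and 28 control patients.

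**The concern.** The three p-values answer different questions. Time is not a comparison between arms. Group compares the average of the two visits, one of which precedes training, so it carries half of any training effect. Only group × time compares change between arms. Because no term is named, the same data can support opposite conclusions depending on which line is read. The statement that type I error is controlled holds for the training question only if one term is designated.

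The planned intervals describe arm means. The interval for a between-arm difference in change also depends on the within-patient correlation, so it cannot be read directly from them. A reader may recover part of the effect from the means and Cohen's d, but the CQ difference and its uncertainty are not stated. Baseline CQ could also narrow that interval, and the plan does not use it as a covariate.

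**Working it through.** **Inputs from the documents.** Two-group comparison of CQ, α = .05, power .80, effect size .80, 26 per group, 30 and 28 analysed (Setting and samples); two visits, baseline and week 12.

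**Assumed, because the documents do not give them.** The baseline-to-week-12 correlation r = .3, .5, .7 and the ratio k = week-12 SD / baseline SD from .8 to 1.5. Scores are taken as normal, with the same SDs and slope in both arms.

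**The plan's own figure.** A two-sided two-sample t test (noncentral t, d = .80) has power 79.1% at 25 per group and 80.7% at 26, so the stated 26 reproduces. At 30/28 the power is 84.9%.

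**Variances**, with baseline SD = 1:
- Change, whose between-arm t test is the group × time test with two visits: 1 + k² − 2rk
- Mean of the two visits (group term): (1 + k² + 2rk)/4, with the effect halved
- ANCOVA: k²(1 − r²) × (1 + 1/(N − 4)); at N = 58 the last factor is 1 + 1/54 = 1.0185, the cost of estimating the slope

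Example at k = 1, r = .5: change 1 + 1 − 1 = 1.00; ANCOVA .75 × 1.0185 = .764; ratio .76.

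**ANCOVA variance divided by group × time variance:**

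| k | r = .3 | r = .5 | r = .7 |
|---|---|---|---|
| .8 | .51 | .58 | .64 |
| 1 | .66 | .76 | .87 |
| 1.2 | .78 | .89 | .98 |
| 1.3 | .82 | .93 | 1.01 |
| 1.5 | .89 | .98 | 1.02 |

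The ratio peaks at k = 1/r, where it equals 1.0185, so on average ANCOVA is never more than 1.9% worse. Simulation at 30/28 (100,000 trials per cell) agrees with the table to within .01.

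**95% CI half-width in week-12 SDs** (r = .3/.5/.7). The standard error multiplier is √(1/30 + 1/28) = .263.
- ANCOVA: .51/.46/.38 at any k
- Group × time: .71/.60/.47 at k = .8; .62/.53/.41 at k = 1; .54/.46/.38 at k = 1.5

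**Power at 30/28 for a week-12 difference of .80 SD.** The standardised effects are .8k/√(1 + k² − 2rk) for group × time, .4k/√((1 + k² + 2rk)/4) for group, and .8/√(1 − r²) for ANCOVA on N − 3 df, averaged over chance baseline imbalance. At k = 1:

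| Term | r = .3 | r = .5 | r = .7 |
|---|---|---|---|
| Group | 45.9% | 40.8% | 36.8% |
| Group × time | 71.5% | 84.9% | 97.1% |
| ANCOVA | 87.4% | 92.8% | 98.6% |

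Over k = .8 to 1.5 the group term stays between 30% and 60%. If the .80 is instead in SDs of change, group × time has 84.9% at any r. The plan is therefore not shown to miss its 80%, but what the sizing implies for group × time depends on an SD it does not state.

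**False positives if group or group × time were accepted, whichever was significant.** The upper bound is 1 − .95² = 9.75% per outcome. Simulation under no effect (400,000 trials per cell) gives 9.07% (k = 1.5, r = .7) to 9.78% (k = 1, r = .3), with Monte Carlo error about .09 points.

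**The case against.** The strongest reply is that group × time is already a valid between-arm test of change. Naming it and reporting the difference in change with its 95% CI would close the gap without a new model, and the gain from ANCOVA is unknown in these data. The validity point stands: the model can test training. The gain may indeed be nil, but the average cost is at most 1.9% of variance and the saving can approach half.

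A second reply is that showing ANCOVA beside group × time recreates the ambiguity. In simulation under no effect, the two disagree on significance in about 4–6% of trials at SD ratios .8 to 1, and at least one is below .05 in about 7–8%. This is answered only if ANCOVA is the single named test and group × time is kept for transparency, whichever result is more favourable.

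Third, the plan states no rule of accepting either term. That is correct, so the 9.75% is conditional. It also covers only those two terms: adding an unadjusted week-12 t test raises it to about 11–12% at SD ratios .8 to 1.

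Fourth, the section's wording suggests that the t and Mann–Whitney tests are for variables not measured twice. That is a natural reading, and the point is only a request for clarity. Finally, ANCOVA does not address the restriction to 58 complete cases out of the 74 included.

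**Conclusion.** The concern holds. The plan designates no test of training and states no interval for the between-arm difference; both are plain from the text and depend on no assumption. The consequence is material: for one and the same effect, power is about 41% on the group term and 85% on group × time (r = .5, equal SDs).

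The case for baseline adjustment is a cheap improvement, not the repair of an invalid test. Its variance relative to group × time runs from .51 to 1.02 over r = .3 to .7 and SD ratios .8 to 1.5, under normal scores with common SDs and slope across arms. The precision gain disappears when r is high and the week-12 SD is clearly larger than the baseline SD. A single named test and a stated interval are still needed in that case. This is a change that should be made.

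**What to change.** - Name one test of training for CQ: ANCOVA of week-12 CQ on arm with baseline CQ as covariate. Report the adjusted difference in CQ points with 95% CI and p-value, and Cohen's d with its SD defined and a 95% CI. Do the same for the other continuous outcomes measured at both visits.
- Show the planned group × time result beside it, as the between-arm difference in change with its 95% CI. Do not present the group p-value as a test of training.
- State which variables and visits the t and Mann–Whitney tests cover, and which test and SD the effect size .80 refers to. These are clarifications; the main change does not depend on them.

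The cost is a few lines of text and one model in the same software, with no new data. The drawback is timing. Data collection has ended and the document already contains a study result (under Compliance questionnaire, "Alpha value of the responses given to CQ was found as .701"), so the ANCOVA must be dated and labelled post hoc.

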## **Disease Management for Coronary Artery Patients**

**Clinical Trial Register Number: NCT04556006**

**Ethics Committee Approval Date: June 6, 2018**

**Document Date: June 17, 2021**

### **Study Protocol**

#### **Setting and samples**

This study was planned as a single-blind randomised controlled trial with pretest–posttest and followed the guidelines of the Consolidated Standards of Reporting Trials (CONSORT) statement. The population of the study was composed of the patients diagnosed with coronary artery disease (CAD) staying in cardiology clinic of a State Hospital in Southeast Anatolia Region, Turkey (March, 2019–March, 2020). The sample size of the study was determined according to the result of the power analysis. The minimum sample size required for the difference to be significant in terms of compliance questionnaire (CQ) scores in patients who received and did not receive training was determined to be at least 26 patients in each group ( $\alpha = .05$ ,  $1 - \beta = .80$ , effect size = .80). The patients, who were aged between 18 and 79, were diagnosed with CAD for at least 2 months, had no hearing and vision problem, had no perception and expression deficiency, were not diagnosed with any psychiatric dis-ease and were voluntary to participate in the study, were included in the study. A total of 74 patients meeting the inclusion criteria (37 in the intervention group and 37 in the control group) were included in the sample. However, the study was terminated within the scope of COVID-19 pandemic measures that started abroad and affected Turkey too. The sample of the study consisted of 58 patients (30 in the intervention group and 28 in the control group) whose data were completely collected until the pandemic period.

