## **Data collection tools**

The data of the participants were collected by using personal information form, anthropometric measurements, Framingham risk score and compliance questionnaire.

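### The trial is sized on CQ alone, but the analysis tests every continuous outcome at .05 and ranks none, so false-positive error across outcomes is uncontrolled

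*Combined protocol and SAP*

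**What the plan says.** **Sizing.** Setting and samples bases the power analysis on one outcome: "The minimum sample size required for the difference to be significant in terms of compliance questionnaire (CQ) scores". With alpha .05, power .80 and effect size .80, the requirement was "determined to be at least 26 patients in each group". The analysed sample was "30 in the intervention group and 28 in the control group".

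**Outcomes.** Data collection tools lists "personal information form, anthropometric measurements, Framingham risk score and compliance questionnaire". Anthropometric measurements specifies height, weight, waist and hip circumference. Second stage says that the baseline forms and measurements were repeated at 12 weeks.

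**Analysis.** Data analysis states that "p- values for continuous variables are obtained from general linear model repeated measures analysis", with group as the between-subject factor and time as the within-subject factor. P-values are reported for group, time and their interaction. The section then says that type I error for variation within and between groups was controlled by this means, and it sets one significance level, p < .05. No section calls any outcome primary or secondary, and no adjustment across outcomes is named.

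**The concern.** The sizing section treats CQ as the outcome that matters, and the analysis section does not carry that through. Under Data analysis as written, if CQ showed no effect and waist circumference gave p = .04, the waist result could be reported as a significant effect of training on the same footing as CQ. No effect size or power was stated for any non-CQ outcome.

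The sentence on type I error makes this worse, because a reader may take it as assurance that multiplicity has been dealt with. A repeated-measures model organises the group and time factors for one outcome. Fitting it separately to several outcomes gives each its own 5% chance of a false positive on any given term.

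**Working it through.** **1. The plan's own figure.** Inputs from Setting and samples: alpha .05 (taken as two-sided), power .80, d = .80, equal groups. The noncentral-t calculation for a two-sample t test gives 26 per group (power 80.7%). A one-sided test would need only 21, so the stated 26 is two-sided. The sample size is not in dispute.

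**2. Number of outcomes (inferred).** CQ, Framingham score, weight, waist and hip make five. Height is left out because it would not change in 12 weeks. BMI and waist–hip ratio are left out because the documents do not say that they were derived. Framingham is taken as a continuous score.

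**3. Independent tests.** With one between-arm test per outcome at .05 and no true effect on any, the chance of at least one p < .05 among k outcomes is 1 − .95^k:

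- k = 5: 1 − .95^5 = 1 − .7738 = 22.6%
- k = 4: 1 − .95^4 = 1 − .8145 = 18.5% (also the figure for the four non-CQ outcomes alone)
- k = 6: 1 − .95^6 = 1 − .7351 = 26.5%

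**4. Correlated tests.** The documents give no correlations, so these are assumed. Five correlated two-sided z tests were simulated under no effect (at least 10^6 draws; standard error at most √(.2 × .8 / 10^6) = 0.04 percentage points).

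| Correlation among weight, waist, hip | Correlation of all other pairs | Chance of any p < .05 |
|---|---|---|
| .5 | 0 | 21.0% |
| .8 | 0 | 18.6% |
| .9 | 0 | about 17.3% |
| .7 | .3 | 18.7% |
| .9 | .3 | 16.5% |
| .9 | .5 | about 15.1% |
| .5 | .5 | 18.3% |
| .7 | .7 | about 14.8% |
| .8 | .8 | 12.7% |
| .9 | .9 | about 10.1% |

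**5. Cost of the remedies in power.** For 30 vs 28 and d = .80:

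- One CQ test at .05: 84.9% power.
- Bonferroni over five outcomes, .05/5 = .01 each: about 65% power. The overall error would be 1 − .99^5 = 4.9% if independent.

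With two time points, the group × time test is the two-sample t test on change scores. The power figures therefore apply if d = .80 describes the between-arm difference in CQ change, in units of its standard deviation. The plan does not say what its effect size is standardised by.

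**The case against.** **CQ is already the evident main outcome.** It is the only outcome that was sized, and the plan also reports confidence intervals and Cohen's d. This is fair as a guide to intent. It does not bind the analysis, which gives CQ no special status.

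**The outcome family is inferred.** Data analysis never lists the variables tested. The account of the final appointment, in the training description after Standard care protocol, mentions only the personal information form and CQ. Anthropometrics are part of that form, but Framingham is not mentioned there. This stands, so five is a working count. If Framingham were dropped, the independent figure would be 18.5%.

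**The rate depends on correlation.** This also stands. A reader who assumes that only weight, waist and hip are correlated would infer a range of 17–23% and treat 17% as a floor. The documents do not support that. The CQ itself covers diet, weight loss and exercise, so it may well move with weight and waist, and rates below 17% follow.

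**Formal testing rules for secondary outcomes are excessive in a small education trial.** This is partly right. Holm testing is not required, and labelling the other outcomes exploratory would be enough.

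**A ranking made now is after the fact.** The document is dated June 2021, the study period ended in March 2020, and the text already reports the number analysed and a Cronbach's alpha from this study. This stands, and calls for disclosure.

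**Conclusion.** The concern holds. The plan sizes on CQ, ranks nothing in the analysis, and claims a control of type I error that does not extend across outcomes. With five outcomes, one between-arm test each and no true effect anywhere, the chance of at least one p < .05 is 22.6% under independence, about 15–21% under moderate to strong correlation, and about 10% if every pair correlates .9. Even that last case is twice the nominal level.

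Three stronger readings are not supported:

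- **That the CQ test is itself inflated.** A single CQ test stays at 5%. The excess lies in claims made across outcomes.
- **That naming CQ primary brings the any-outcome rate to 5%.** It holds only the primary claim at 5%. The any-outcome claim rate is held there only if the other outcomes carry no claim, or are tested under control after a significant CQ result.
- **That outcomes were chosen after the results were seen.** The document's date makes disclosure necessary, but nothing in the text shows selection.

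**What to change.** Add to Data analysis wording to this effect:

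- The single primary test is the group × time term for CQ total score, baseline to 12 weeks, at two-sided .05.
- Framingham score, weight, waist and hip circumference are secondary or exploratory. They are reported as between-arm differences with 95% confidence intervals and no confirmatory significance claim.
- If claims on those four are wanted, they are tested by Holm's procedure only when CQ is significant (smallest threshold .05/4 = .0125).
- This ranking was set after data collection and rests on the CQ sample-size calculation.

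The sentence on type I error should be limited to what the model does within one outcome.

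The change is to wording only and needs no extra patients. It keeps full alpha for CQ, where splitting alpha over five outcomes would reduce power at d = .80 from 84.9% to about 65%. The downside is that an isolated p < .05 on a non-CQ outcome can no longer be claimed as an effect of training. Because the ranking is retrospective, it will also carry less weight than one fixed before data collection.

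### The plan says its repeated-measures model controlled type I error, but the model controls each F test only, and no term is named as the test of training on CQ

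*Combined protocol and SAP*

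**What the plan says.** In the Data analysis section, continuous variables measured at baseline and 12 weeks go into a general linear model with group as the between-subject factor and time as the within-subject factor. The output includes "p- values for group, time and group × time interaction". The next sentence reads "In this way, type I error rate within- and between-groups variation was controlled". A single threshold applies throughout: "Statistical significance level was accepted as" p < .05. Cohen's d "was used for measure of the magnitude of the experimental effect", with no statement of which contrast it describes. The same section also lists an independent-samples t test or Mann–Whitney test for comparing two groups, without saying which variables or time points these serve.

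The Setting and samples section sizes the trial "for the difference to be significant in terms of compliance questionnaire (CQ) scores" between trained and untrained patients. With alpha .05, power .80 and effect size .80, the minimum "was determined to be at least 26 patients in each group". No model term or time point is attached to that comparison. The analysed sample is 58 patients (30 intervention, 28 control) "whose data were completely collected until the pandemic period".

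The document gives no testing order, alpha split or multiplicity adjustment.

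**The concern.** The phrase that opens the error-control sentence credits the control to what comes just before it, namely reporting three p-values from one model. Fitting one model does not do that. Each F test has its own 5% level, and the chance that at least one of several is significant is larger.

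This matters because the plan leaves open which result would count as an effect of training on CQ. Two of the three terms compare the arms, and they answer the question with very different sensitivity. The third does not compare the arms at all. A reader who takes the sentence at face value may believe the conclusion about training is held at 5%, when that is so only if one test was designated to carry it.

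**Working it through.** **Inputs from the document.** Alpha .05, power .80, effect size .80 and 26 per group (Setting and samples); 30 v 28 analysed (same section); two time points, three p-values and p < .05 (Data analysis).

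**Assumptions.** The document gives no CQ standard deviations and no pre-post correlation ρ. The check uses ρ = .3, .5 and .8 for power, and a range of post/pre SD ratios for error. The Compliance questionnaire section quotes an "intraclass correlation coefficient value .69" from a validation study, but its type is not stated, so it is not used as ρ.

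**1. The plan's own figure.** A two-sided two-sample t test with d = .80 and alpha .05 (noncentral t) gives power .791 at 25 per group and .807 at 26. The stated 26 is reproduced by a single two-sided between-arm test. A one-sided test would need 21.

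**2. What the terms are.** With two arms and two times:
- group is a t test on pre + post (56 df);
- group × time is a t test on post − pre (56 df);
- time tests the average change over both arms.

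**3. Error if either between-arm term may count.** Cov(post + pre, post − pre) = Var(post) − Var(pre). With equal variances this is zero, so under no effect and normality the two tests are independent apart from small-sample detail:
- one named term: 5%;
- group or group × time: 1 − .95² = .0975.

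Null simulation at 30 v 28 (200,000 runs per setting, ρ from 0 to .9), with each term alone at about 5%:

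| Post/pre SD ratio | Either term significant |
|---|---|
| 1 | 9.7–9.8% |
| 1.25 | 9.4–9.7% |
| 1.5 | 8.5–9.3% |
| 2 | 7.4–8.8% |

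A ratio of 0.5 gives 8.0–8.5% for ρ = .3 to .8 (100,000 runs per setting). The Bonferroni bound is 10%.

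**4. Why the choice of term matters.** Read the effect size of .80 as a 12-week difference of 0.8 SD (an assumption), with equal SDs. Standardised effects are:
- group: 0.4/√((1 + ρ)/2), because averaging with the baseline halves the 12-week difference;
- group × time: 0.8/√(2(1 − ρ));
- baseline-adjusted 12-week difference: 0.8/√(1 − ρ²).

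Noncentrality = effect × √(30 × 28/58) = effect × 3.806.

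| ρ | Group: effect, power | Group × time: effect, power | Baseline-adjusted: effect, power |
|---|---|---|---|
| .3 | .496, 46% | .676, 72% | .839, 88% |
| .5 | .462, 41% | .800, 85% | .924, 93% |
| .8 | .422, 35% | 1.265, 99.7% | 1.333, 99.9% |

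**5. The time term.** Suppose both arms improve equally by 0.3 SD (an illustrative value). The standardised change is 0.3/√(2(1 − ρ)), with noncentrality multiplier 2/√(1/30 + 1/28) = 7.61. The time term is then significant in 61% of trials at ρ = .5 and 94% at ρ = .8, with no training effect present.

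**The case against.** The sentence is loosely worded and need not be a claim of familywise control. It follows an explanation that measurements were repeated, and may mean only that one model replaces separate within-arm and between-arm tests. The plan also commits to reporting all three p-values separately, with means and 95% confidence intervals, so a reader can see which term was significant. Both points are fair and limit the weight of the finding. They do not rescue the sentence, because the stated mechanism does not deliver control beyond the individual test, and seeing three p-values does not tell a reader which was meant to decide.

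It can also be said that group × time is the obvious test. It may have been intended, but the plan does not say so. The sample-size comparison of trained with untrained patients fits either between-arm term, and Cohen's d is tied to neither.

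Some stronger readings are tempting, and the document does not support them:
- *The trial's error rate is 9.75%.* That needs an either-term decision rule, which appears nowhere in the plan, and roughly equal pre and post SDs.
- *It is 14.3%, counting all three terms (1 − .95³).* Time does not compare the arms, so it is not a test of training.
- *The trial is underpowered.* The low power in step 4 belongs to the group term only, and rests on reading .80 as a 12-week difference. The plan gives neither a time point nor a scale for it.
- *The group term is invalid.* Under randomisation it is a valid test, only diluted by the baseline.

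**Conclusion.** The concern holds. The plan attributes to its model a property the model does not have, and leaves the decisive CQ test unnamed. The consequence for error is conditional: up to about 9.75% if either between-arm term could be taken as a training effect, about 8% if the pre and post SDs differ twofold, and 5% if one term is named. These figures cover CQ only. They leave out other continuous outcomes and any additional t or Mann–Whitney comparison of CQ.

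That the terms are not interchangeable does not depend on the either-term assumption. The power figures do depend on the assumed correlations and on the reading of .80, but across ρ = .3 to .8 the ordering is the same: the baseline-adjusted difference has the most power, then group × time, then group. At ρ = .3 group × time falls below the planned 80%, so it and the baseline-adjusted difference should not be treated as equivalent choices.

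**What to change.** - Delete the error-control sentence, or restate it as: *each F test is held at 5%; no control across tests is claimed*.
- Name one CQ test of training at two-sided .05: the baseline-adjusted 12-week difference between arms (ANCOVA on the baseline CQ already collected). Offering a choice of tests would reopen the problem.
- Report Cohen's d for that same contrast.
- Keep group × time and group as supportive, noting that group is diluted by the pre-training baseline. State that the time effect is not evidence of training.
- Date the choice and disclose that it was made after data collection.

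The cost is some rewording and one additional model on existing data, with no new measurements. The drawback is that p-values from the other terms no longer carry the conclusion, and a post hoc choice cannot restore a pre-specified 5% level.
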